# 5 STUDY AGENT

### 5.1 Description

rAAV2tYF-CB-hRS1 is a non-replicating, rep/cap-deleted, recombinant adeno-associated virus (rAAV) vector containing cDNA encoding the human retinoschisin (RS1) protein.

The vector contains AAV serotype 2 inverted terminal repeats and an expression cassette consisting of a CMV enhancer/chicken beta actin promoter, the human RS1 cDNA and an SV40 polyadenylation sequence, and is packaged in an AAV2 capsid containing tyrosine to phenylalanine (YF) mutations in three surface-exposed tyrosine residues (AAV2tYF).

The organization of the elements in the DNA molecule is depicted in Figure 2 below.

#### Figure 2 Organization of the rAAV2tYF-CB-hRS1 vector

ITR = inverted terminal repeat, CB = CMV enhancer/chicken beta actin promoter, RS1 = retinoschisin, pA = polyadenylation signal

rAAV2tYF-CB-hRS1 was manufactured in compliance with current Good Manufacturing Practices (cGMP) under contract to Applied Genetic Technologies Corporation (AGTC).

### 5.2 Study Agent Storage and Stability

The study agent is provided as a sterile frozen liquid and must be stored at -65°C or below. Stability testing indicates rAAV2tYF-CB-hRS1 is stable for up to 3 years when stored at this temperature.

### 5.3 Study Agent Preparation and Dosage Levels

Three dose levels of rAAV2tYF-CB-hRS1, administered by intravitreal injection, will be evaluated in this clinical protocol. The lower dose level will be  $1 \times 10^{11}$  vector genomes (vg) per eye (0.07 mL at  $1.43 \times 10^{12}$  vg/mL). The middle dose level will be  $3 \times 10^{11}$  vg per eye (0.07 mL at  $4.3 \times 10^{12}$  vg/mL). The higher dose level will be  $6 \times 10^{11}$  vg per eye (0.14 mL at  $4.3 \times 10^{12}$  vg/mL).

Research pharmacy personnel will thaw and dilute and prepare the study agent to the correct concentration and volume according to instructions provided in the study Pharmacy Manual.

The syringe(s) containing study agent will then be maintained at 2-8°C and delivered to a designated area in the administration room. Study agent administration should occur within 4 hours of thawing and preparation.

# 5.4 Study Agent Administration

The participant may be started on steroids prior to the study agent administration as described in the Study Manual of Procedures.

Immediately prior to study agent administration, the participant will be placed in the supine position and the participant's eye will be prepared for injection by applying topical anesthetic and/or subconjunctival anesthetic followed by povidone-iodine. A povidone-iodine solution will then be used to cleanse the eyelids. A sterile speculum will be inserted to separate the lids.

Prior to injection the povidone-iodine solution will be reapplied to the injection site. A cotton swab soaked in topical anesthetic can be used to soften the eye prior to injection. Care should be taken not to express secretions from the meibomian glands in the lids.

Sedation for the intraocular injection may be used at the discretion of the investigator to insure that the intravitreal injection can be completed in a safe manner.

The participant will be instructed to direct his or her gaze away from the site of needle entry. After the needle penetrates the sclera the needle is advanced toward the center of the globe and the fluid is gently injected into the mid- to posterior vitreous cavity. The needle is removed and a sterile cotton swab is immediately placed over the injection site to prevent reflux.

For participants receiving the high dose in a volume of 0.14 mL, it is preferable to administer a single injection as it decreases the infection risk and it is more comfortable for the patient. However; the Investigator should confirm that there is perfusion of the retina after injection and be prepared to address unusually high or prolonged increase in IOP, if needed. Performing an anterior chamber tap (paracentesis) before this single injection is at Investigator's discretion. If the dose is alternatively administered as two injections of 0.07 mL, the optic disc should be visualized after the first 0.07 mL is injected to confirm that there is perfusion of the retina, before the second 0.07 mL is injected.

After study agent administration is completed, the participant will remain in the supine position and the IOP will be measured about 30 minutes after the injection. The participant will remain under direct observation until the IOP returns to a value less than 30 mm Hg. Prolonged or unusually high IOP will be managed using standard methods at the discretion of the investigator.

The participant will be instructed to notify the investigator immediately if symptoms of eye pain, redness, photophobia or diminished vision develop.

### 5.5 Dose-limiting Toxicity

- Every AE recorded in this study must be assessed by the investigator to determine whether or not it meets the definition of a dose-limiting toxicity (DLT).
- A DLT is defined as any toxicity determined by the investigator to be related to the study agent and deemed serious or sufficiently severe to preclude dose escalation.
- For the purpose of this study, any grade 4 or 5 event (per the Common Terminology Criteria for Adverse Events (CTCAE) v4.0 criteria) that is assessed as possibly, probably or definitely related to the study drug will be considered to be a DLT.

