Enrollment will begin with Group 1A and will proceed to subsequent groups after review of safety data by the DSMC. After review of safety data from Group 1A, participants will be enrolled in Groups 1B and 2 concurrently. After review of safety data from Groups 1A, 1B and 2, participants will be enrolled in Group 3. After review of safety data from Groups 1A, 1B, 2 and 3, participants  $\geq$ 18 years of age will be enrolled in Group 4. As ocular inflammation has been seen in the first 12 subjects enrolled in the study and pediatric participants might be more prone to inflammation, pediatric participants (age 6-17) in this study will first be treated at the middle dose (Group 2A) prior to the enrollment in Group 4.

Within groups 1A, 1B, 2, 2A, and 3, enrollment of participants will be staggered by at least 2 weeks to allow adequate time for review of safety information by the investigators and sponsor.

Within Group 4, enrollment of the first 3 pediatric participants will be staggered by at least 2 weeks to allow adequate time for review of safety information by the investigators and sponsor.

Safety will be monitored by evaluation of ocular and non-ocular AEs, hematology and clinical chemistry parameters and immune responses to RS1.

Efficacy will be measured by evaluation of visual acuity, visual fields, microperimetry, contrast sensitivity, reading speed, OCT with infrared montage, to include volumetric analysis of schisis cavity size, ERG, and quality of life questionnaires.

Other data collected will include fundus photography, immune responses to AAV and the presence of vector DNA in blood.

Approximately 27 participants will be enrolled in this study. Enrollment in this study is anticipated to take approximately 30 months. Enrolled participants will have frequent follow-up visits during the first year after study agent administration.

To monitor for delayed AEs and assess the duration of any changes in visual function or structure that occur, participants will be followed annually for an additional 4 years after the Month 12 visit.

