#### 7.2.1.3 Relationship to Study Agent

The investigator's assessment of an AE's relationship to study agent is part of the documentation process, but it is not a factor in determining what is or is not reported as an AE in the study. If there is any doubt as to whether a clinical observation is an AE, the event should be reported. All AEs must have their relationship to study agent assessed using the following terms: associated or not associated. "Associated with the use of the study agent" means that there is a reasonable possibility that the experience may have been caused by the study agent [61]. In a clinical trial the study agent must always be suspect. To help in assessing the relationship to study agent, the following guidelines are used.

- **Associated** The event is temporally related to the administration of the study agent and no other etiology explains the event.
- **Not Associated** The event is temporally independent of study agent and/or the event appears to be explained by another etiology.

Events assessed as being associated with study agent will be further classified as possibly, probably or definitely related to study agent.

Events assessed as being not associated with study agent will be further classified as probably not or definitely not related to study agent.

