#### 7.2.1.4 Relationship to Intravitreal Injection Procedure

All AEs will also be assessed for their relationship to the intravitreal injection procedure used to administer the study agent, using the same categories as described in Section 7.2.1.3.

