#### 7.3.2 Serious Adverse Events

All AEs that meet the criteria for an SAE as defined in Section 7.2.1.5 must be reviewed and evaluated by a study physician and captured on the appropriate SAE eCRF. The SAE eCRF must be complete within the following timelines:

- Every AE with onset during or after study agent administration that meets the protocol defined criterion for a designation of serious or a DLT must be reported to the Sponsor by recording on the subject's AE eCRF within 24 hours of the Investigator or study staff's first knowledge of the event.
- Entry of SAE or DLT information in the eCRF will trigger an e-mail to the Sponsor to take appropriate action in response to the information.
- In any instance in which the database cannot be accessed, a paper SAE form must be completed and faxed to the Sponsor (at AGTC [contact]), followed by a phone call within 24 hours of the Investigator or study staff's first knowledge of the event.

A separate set of SAE eCRF pages should be used for each SAE. However, if at the time of initial reporting, multiple SAEs are present that are temporally and/or clinically related, they may be reported on the same SAE eCRF page.

DLT reporting will follow the same timeline as SAE reporting.

The investigator should attempt to establish a diagnosis of the event based on signs, symptoms, and/or other clinical information. In such cases, the diagnosis should be documented as the AE and/or SAE and not the individual signs/symptoms. New or updated information should be recorded on the originally completed SAE eCRF pages.

If a subject dies during participation in the study, a copy of any post-mortem findings, including histopathology, should be provided when available as an attachment to an updated SAE eCRF page.

Other supporting documentation of the event may be requested and should be provided as soon as possible.

Questions about SAE reporting can be referred to [name] at AGTC [contact], [name].

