### 7.3.3 Regulatory Reporting

Following notification from the investigator, the sponsor will report events that are both serious and unexpected and that are associated with study agent to the US Food and Drug Administration (FDA) within the required timelines as specified in 21 CFR 312.32, *i.e.*, fatal and life-threatening events within 7 calendar days (by telephone or fax) and all other SAEs in writing within 15 calendar days. These SAEs will also be reported to the Institutional Review Board (IRB) at each site, the NIH Office of Biotechnology Activities, and other site-specific committees according to regulatory requirements. SAEs designated as not associated with study product will be reported in a summary format to the DSMC during each between-cohort review and to the FDA at least annually.

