# 7.4 Data and Safety Monitoring Plan

#### 7.4.1 Temporary Suspension of Study Agent Administration

Within groups 1A, 1B, 2, 2A, and 3, enrollment of participants will be staggered by at least 2 weeks to allow adequate time for review of safety information by the investigators and sponsor. Within group 4, enrollment of the first 3 pediatric participants in each group will be staggered by at least 2 weeks to allow adequate time for review of safety information by the investigators and sponsor. If any participant within any study group develops a dose-limiting toxicity (as defined in Section 5.5), enrollment of additional participants will not proceed until review by the DSMC.

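### The only event-triggered enrollment hold requires relation to the study agent, so a serious or Grade 4-5 event attributed solely to the injection or the anterior chamber tap does not require a pause

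*Protocol*

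**What the plan says.** Protocol 5.5 gives the DLT definition two clauses, and both depend on the agent. The general clause reads: "A DLT is defined as any toxicity determined by the investigator to be related to the study agent and deemed serious" or severe enough to rule out escalation. The second makes a CTCAE Grade 4 or 5 event a DLT if it is at least possibly related to the study drug. SAP 14.1 repeats both clauses.

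Protocol 7.4.1 attaches the hold to that definition: "If any participant within any study group develops a dose-limiting toxicity (as defined in Section 5.5), enrollment of additional participants will not proceed" until the DSMC has reviewed. Section 5.6 says the same. Neither section names another event that stops enrollment.

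Relation to the procedure is rated separately under 7.2.1.4: "All AEs will also be assessed for their relationship to the intravitreal injection procedure used to administer the study agent". SAP 14.1 uses that rating for summary tables only.

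On reporting, 7.3.3 says: "SAEs designated as not associated with study product will be reported in a summary format to the DSMC during each between-cohort review". The four DSMC reviews in 5.6 and 7.4.2 follow the last participant in Group 1A, in Groups 1B and 2, in Group 3, and in Group 2A.

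On spacing, Groups 1A, 1B, 2, 2A and 3 are staggered by at least 2 weeks (5.6). For Group 4, Protocol section 3 says only: "Within Group 4, enrollment of the first 3 pediatric participants will be staggered by at least 2 weeks".

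**The concern.** Intravitreal injection can cause serious harm that has nothing to do with the vector. Protocol 1.3.1 lists retinal tears, detachment, hemorrhage and infection as risks of any intravitreal injection, and hypotony, hyphaema and endophthalmitis as risks of the tap. Section 1.2.1 adds that XLRS retinas are unusually fragile. If the investigator attributes such an event wholly to the needle or the tap, it is not a DLT, however severe, and no rule makes the next participant wait.

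This also bears on choosing the dose. The middle and high doses use the same concentration (4.3 × 10^12 vg/mL); the high dose is reached by doubling the volume from 0.07 to 0.14 mL. The tap is an option only before the single 0.14 mL injection (5.4). Serious harm from that volume or from the tap is relevant to whether the dose is tolerable, yet it escapes the DLT rule if it is classed as procedural.

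**Working it through.** This is mainly a check of how the rules fit together. The arithmetic only shows scale.

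**1. Trace a procedure-only event through the rules.** Take a Grade 4 event in a Group 4 adult that the investigator attributes to the needle alone.

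- *Agent rating (7.2.1.3).* An event counts as associated if "The event is temporally related to the administration of the study agent and no other etiology explains the event". Here the needle explains it, so it is not associated.
- *DLT (5.5).* Both clauses need relation to the agent or drug. Not a DLT.
- *Hold (5.6, 7.4.1).* No DLT, so no required hold.
- *Procedure rating (7.2.1.4).* Recorded, but no hold rule uses it. A tap-only event has no category of its own, because this section names only the injection procedure.
- *Sponsor notice (7.3.2).* "Entry of SAE or DLT information in the eCRF will trigger an e-mail to the Sponsor", within 24 hours if the event is serious. This is notice, not a hold.
- *DSMC (7.3.3).* If serious, the event is summarized at a between-cohort review. None of the four is keyed to Group 4. The fourth covers all enrolled participants, so it may include Group 4 adults dosed by then, but only incidentally.
- *Stagger.* None for Group 4 adults.

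**2. The plan's own figures.** Protocol 10.5 gives exact two-sided 95% upper limits for zero DLTs, 1 − 0.025^(1/n):

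- n = 9: 1 − 0.025^(1/9) = 33.63%
- n = 27: 1 − 0.025^(1/27) = 12.77%

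Both reproduce and neither is disputed. They bound the rate of DLTs as defined, so zero DLTs says nothing about procedure-only events.

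**3. Size of Group 4.** The schematic allows up to 15; the total is about 27. Groups 1A, 1B, 2 and 3 take 3 + 3 + 3 + 3 = 12. With a full Group 2A, 27 − 12 − 6 = 9 remain; with none, 27 − 12 = 15. The adult share is not stated, so 3 and 6 are also shown.

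**4. Chance of at least one procedure-only serious or Grade 4-5 event, 1 − (1 − p)^n.** The documents give no p; all four rates are assumptions.

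| n | p = 0.5% | 1% | 2% | 5% |
|---|---|---|---|---|
| 3 | 1.5% | 3.0% | 5.9% | 14.3% |
| 6 | 3.0% | 5.9% | 11.4% | 26.5% |
| 9 | 4.4% | 8.6% | 16.6% | 37.0% |
| 15 | 7.2% | 14.0% | 26.1% | 53.7% |

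What the documents do say points to the low end: no volume-related AEs in macaques at 110 µL (1.2.2), and infection described as uncommon (1.3.1).

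**5. Participants still undosed at the first event.** Given at least one event, the mean is Σ(n − k)·p·(1 − p)^(k−1) / [1 − (1 − p)^n], summed over k = 1 to n. Across the four rates this is 4.0 to 4.3 for n = 9 and 7.1 to 7.9 for n = 15. It assumes one-at-a-time dosing and immediate recognition, so it is an upper guide to how many a hold could protect.

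**6. Expected procedure-only events, n × p, as a guide to extra holds.**

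| n | p = 0.5% | 1% | 2% | 5% |
|---|---|---|---|---|
| 9 | 0.045 | 0.09 | 0.18 | 0.45 |
| 15 | 0.075 | 0.15 | 0.30 | 0.75 |
| 27 | 0.135 | 0.27 | 0.54 | 1.35 |

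The n = 27 row assumes the same rate at every dose. Events rated related to both agent and procedure are left out, because they can already be DLTs.

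**The case against.** The strongest reply is that a DLT exists to limit dose, so tying it to the agent is ordinary practice and contradicts nothing in either document. That stands: this is a suggested improvement, not an error.

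Second, the remaining class of events is small. Section 7.2.1.3 also says "In a clinical trial the study agent must always be suspect", a rating of possibly related is enough, and agent and needle enter the eye together. Inflammation, retinal breaks and detachment appear in 1.3.1 as risks of both. Many serious ocular events, including a volume-driven pressure rise, could be rated possibly agent-related and become DLTs. This stands too, and limits the point to events attributed to the procedure alone.

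Third, other controls exist: 24-hour SAE notice, ongoing review by investigator and sponsor (1.3.2), the power of investigators, sponsor, DSMC or FDA to lengthen dosing intervals, the perfusion and pressure checks in 5.4, and DSMC review of Group 3 at 0.14 mL before adults enter Group 4. A reader might infer that procedural harm goes unmonitored or that dosing would carry on regardless. The documents do not support that. They make the pause discretionary rather than required.

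A reader might also infer that a DLT is the only thing that ever stops enrollment, or that Group 4 has no automatic protection. Neither is so: planned DSMC reviews also stop enrollment between groups, and an agent-related DLT in Group 4 triggers the hold.

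Finally, a hold cannot protect adults dosed before a delayed event is recognized. That is true without an adult stagger, and the fix below does not add one.

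**Conclusion.** The point holds in limited form. The only event-triggered hold depends on relation to the agent, so a serious or Grade 4-5 event attributed solely to the injection or tap does not require a pause. The exposure is greatest for Group 4 adults and for the 0.14 mL dose; in Group 4 the tap matters only if the MTD is that dose.

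Its size cannot be fixed from the documents. The probabilities are illustrative and describe an event falling outside the trigger, not dosing wrongly continuing. They mix adults with children, who may receive 0.07 mL.

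Two limits remain. The Study Manual of Procedures and any DSMC charter were not available and could contain a stopping rule. The version 8.0 entry in Appendix C cites a 12-month analysis, so dosing may be complete. In that case the hold has nothing to act on.

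**What to change.** Keep the DLT definition in 5.5 unchanged, and make three edits.

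1. In 5.6 and 7.4.1, add: *If any participant in any group, including Group 4, has a serious or CTCAE Grade 4 or 5 event rated possibly, probably or definitely related to the intravitreal injection procedure, no further participant is enrolled until the DSMC has reviewed it.*
2. In 7.2.1.4, state that an anterior chamber tap counts as part of the injection procedure.
3. In 10.7.5, require the summary prepared before each DSMC review to show these events by dose and injected volume. That summary is what the committee sees when the MTD is decided; SAP Listing 16.2.7.4 covers DLTs only and is not the right vehicle.

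The cost is protocol wording and one added display. The rating is already collected for every AE, no new committee is needed, and the decision after review stays with the DSMC. The downside is an occasional short pause for a routine injection complication, because 7.2.1.5 counts as serious any event that needed intervention to prevent permanent damage. If dosing has finished, edit 2 is still worth making, so that tap events enter the SAP's injection-related tables (14.3.7, 14.3.8 and 14.3.11).

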### 5.6 Dosing Plan

Within Groups 1A, 1B, 2, 2A, and 3, enrollment of participants will be staggered by at least 2 weeks to allow adequate time for review of safety information by the investigators and sponsor.

Within group 4, enrollment of the first 3 pediatric participants in each group will be staggered by at least 2 weeks to allow adequate time for review of safety information by the investigators and sponsor.

If any participant within any study group develops a dose-limiting toxicity (as defined in Section 5.5), enrollment of additional participants will not proceed until review by the DSMC.

Enrollment will begin with Group 1A and will proceed to subsequent groups after review of safety data by the DSMC. After review of safety data from Group 1A, participants will be enrolled in Groups 1B and 2 concurrently. After review of safety data from Groups 1A, 1B and 2, participants will be enrolled in Group 3. After review of safety data from Groups 1A, 1B, 2 and 3, participants  $\geq$ 18 years of age will be enrolled in Group 4. As ocular inflammation has been seen in the first 12 subjects enrolled in the study and pediatric participants might be more prone to inflammation, pediatric participants (age 6-17) in this study will first be treated at the middle dose (Group 2A) prior to the enrollment in Group 4.

Each safety review will be conducted based on data for all enrolled participants accrued up to and including the visit 2 weeks after administration of rAAV2tYF-CB-hRS1 to the last participant enrolled in Group 1A (for the first review), 2 weeks after administration of rAAV2tYF-CB-hRS1 to the last participant enrolled in Groups 1B and 2 (for the second review), 2 weeks after administration of rAAV2tYF-CB-hRS1 to the last participant enrolled in Group 3 (for the third review), or 2 weeks after administration of rAAV2tYF-CB-hRS1 to the last participant enrolled in Group 2A (for the fourth review), The length of time between dosing participants may be extended if the investigators, sponsor, DSMC or FDA believes that additional time is needed to ensure safety of the participants. (See Section 7 for additional information on safety monitoring.)

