#### 1.1.4.3.2. Safety and biodistribution in cynomolgus macaques

In the nonhuman primate study, three groups of male macaques (n = 6 per group) each received an intravitreal injection of 110  $\mu$ L containing rAAV2tYF-CB-hRS1 at a concentration of 3.6 x 10^11 vg/mL (4 x 10^10 vg per eye) or 3.6 x 10^12 vg/mL (4 x 10^11 vg per eye) or 110  $\mu$ L of vehicle control. Half the animals were sacrificed 14 days after vector administration and the remaining animals were sacrificed 90 days after vector administration.

The intravitreal injection procedure was well tolerated in all groups. Ocular exams demonstrated varying levels of inflammation over time.

In the vehicle control group, aqueous cells ranged from trace to 4+ at 1 week after injection and resolved by Week 2. Vitreous cells ranged from trace to 2+ at 2 to 3 weeks after injection, resolved by Week 4 in four animals and in the other two animals were resolved or resolving at Week 12. None of the animals in this group had vitreous haze.

Ocular inflammation was greater in the vector-treated animals and was more pronounced at the higher dose. Aqueous cells ranged from 1+ to 4+ at Week 1 in all animals, resolved by Week 2, recurred at Week 2 to 4 in two animals in the low dose and three animals in the high dose group, and then resolved over the next several weeks. Vitreous cells developed in 5 of 6 animals in the low dose and all animals in the high dose group, and persisted at 2+ or greater for more than 4 weeks in two animals in the low dose and three animals in the high dose group. Vitreous haze developed at Week 4 in one animal in the low dose and three animals in the high dose group.

The frequency, magnitude and time course of ocular inflammation at doses of  $4 \times 10^{10}$  and  $4 \times 10^{11}$  vg/eye in this study was similar to that seen in a toxicology study of an AAV2 vector expressing a vascular endothelial growth factor receptor inhibitor delivered by intravitreal injection at a dose of  $2.4 \times 10^{10}$  vg/eye [56]. When that product was evaluated by intravitreal injection in a human clinical trial, ocular inflammation developed in 1 of 11 subjects who received the  $2.4 \times 10^{10}$  vg dose, which was treated with topical steroids for 5 weeks during which time it resolved [57].

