There was no apparent effect of vehicle control or rAAV2tYF-CB-hRS1 at either dose level on intraocular pressure, and no changes in ERG or visual evoked potential responses.

There were no intergroup differences in hematology, coagulation or clinical chemistry parameters and no test article-related gross necropsy observations.

Microscopic pathology results demonstrated RS1 labelling of the ganglion cell layer at the foveal slope and minimal or moderate mononuclear infiltrate at the optic disc and/or around blood vessels in the ganglion cell layer, iris, and ciliary body of the injected eye at both dose levels. RS1 labelling of the ganglion cell layer at the foveal slope was observed in all animals at the higher dose and in 5 of 6 animals at the lower dose. Mononuclear infiltrates at the optic disc and/or around blood vessels in the ganglion cell layer, iris, and ciliary body of the injected eye was observed in 2 of 6 animals at the lower dose and 4 of 6 animals at the higher dose. Results of biodistribution testing detected vector DNA in the injected eye but minimal or no vector DNA was found in any other tissue.

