#### 1.2.2 Rationale for Dosage Level

Administration of rAAV2tYF-CB-hRS1myc at a dose of  $1 \times 10^{11}$  vg per eye by intravitreal injection in nonhuman primates demonstrated expression of RS1myc protein in the macula and fovea. Administration of rAAV2tYF-CB-hRS1 at a dose of  $4 \times 10^{10}$  or  $4 \times 10^{11}$  vg per eye by intravitreal injection in nonhuman primates demonstrated ocular inflammation that was maximal 4 weeks after administration and progressively improved over the ensuing 2 months. At sacrifice, microscopic pathology results demonstrated RS1 labelling of the ganglion cell layer at the foveal slope in 5 of 6 animals in the lower dose group and all animals in the higher dose group. Microscopically evident inflammatory cells, usually minimal and occasionally moderate in intensity, were seen in 2 of 6 injected eyes in the lower dose group and 4 of 6 injected eyes in the higher dose group. The volume of a human eye is approximately 5 mL and the volume of a nonhuman primate eye is approximately 2.5 mL. Based on this information, it is concluded that dose levels between  $1 \times 10^{11}$  vg per eye and  $6 \times 10^{11}$  vg per eye are predicted to have the potential for providing benefit with an acceptable safety profile.

Administering the dose in a volume of 70  $\mu$ L or 140  $\mu$ L is considered to be an acceptable volume in human eyes, and is in line with the 110  $\mu$ L volume used in nonhuman primate studies with no AEs related to the injection volume.

The dose escalation schedule is typical of Phase 1 trials of gene therapy products for orphan diseases. Enrolling subjects with the most advanced disease in Group 1A will provide a favorable risk-benefit profile for the product and study procedure. If the safety evaluations identify no dose-limiting toxicity in Group 1A, subjects with less severe disease will be appropriate for enrollment at the next higher dose (Group 2). Subjects with less severe disease will also be enrolled in Group 1B, at the same dose level as Group 1A, in order to increase the ability to detect evidence of efficacy at this dose level. If the safety evaluations identify no dose-limiting toxicity in Group 2, subjects with less severe disease will be appropriate for enrollment at the highest dose level (Group 3). If the safety evaluations identify no dose-limiting toxicity in Group 2A, it will be appropriate to enroll subjects in Group 4.

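### Each between-group DSMC review can proceed on the last participant's Week 2 data, before the 4-week maximum of primate ocular inflammation; Month 1 is a cheap minimum for any review still to come

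*Protocol*

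**What the plan says.** Protocol Section 5.6 sets the data cut for four reviews (after Group 1A, after 1B and 2, after 3, after 2A): "Each safety review will be conducted based on data for all enrolled participants accrued up to and including the visit 2 weeks after administration" to the last participant. Section 7.4.2 repeats this. Section 10.7.5 words it as a floor for the DSMC summary, and the replacement rule in Section 4.3 is tied to the same visit. The SAP (Sections 17 and 18) sets no other timing.

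Section 1.2.2 says that the primate doses "demonstrated ocular inflammation that was maximal 4 weeks after administration and progressively improved over the ensuing 2 months". Section 1.1.4.3.2 shows two phases.

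- **Early, in vector animals:** "Aqueous cells ranged from 1+ to 4+ at Week 1 in all animals, resolved by Week 2". Vehicle animals had it too: "In the vehicle control group, aqueous cells ranged from trace to 4+ at 1 week after injection and resolved by Week 2".
- **Later, in vector animals:** aqueous cells "recurred at Week 2 to 4 in two animals in the low dose and three animals in the high dose group", and "Vitreous haze developed at Week 4 in one animal in the low dose and three animals in the high dose group". Of the vehicle animals the protocol says "None of the animals in this group had vitreous haze".

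Appendix A places eye examinations at Days 1, 7 and 14 and next at Month 1.

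**The concern.** The Day 1, 7 and 14 examinations cover the early phase, which the injection alone also produced. The phase that set vector apart from vehicle came later. For the last-dosed participant the required data stop at half the 28 days at which primate inflammation was greatest.

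The vector is given once and cannot be withdrawn. Reviews 1 and 2 precede dose increases. Review 3 opens adult Group 4. Review 4 opens Group 4 to children, whom the protocol regards as possibly more prone to inflammation. The reviews also inform the choice of MTD. The primary safety parameter covers 12 months (Section 7.1.1), so only these interim decisions are affected.

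**Working it through.** The plan gives no figure for follow-up at each review, so there is none to reproduce. Its DLT confidence limits (Section 10.5) do not bear on this point.

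**Inputs.** Data cut at the last participant's day 14 and a stagger of at least 14 days (Section 5.6); group sizes 3, 3, 3, 3 and up to 6 (Section 3); primate maximum at day 28 (Section 1.2.2); eye volumes 5 mL human and 2.5 mL primate (Section 1.2.2); eCRF entry within 5 business days (Section 14.2); about 30 months of enrollment (Section 3). Assumption: Month 1 falls between day 28 and day 30, because visit windows are in a manual not provided.

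**Follow-up at the cut.** With stagger s, a group of three has 14 + 2s, 14 + s and 14 days. At s = 14 this is 42, 28 and 14. A longer stagger lengthens the first two only; s = 34 gives 82, 48 and 14.

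| Review | Follow-up in days at s = 14 | At day 28 or later |
|---|---|---|
| 1 | 42, 28, 14 | 2 of 3 |
| 2 | 1A: 84, 70, 56; 1B and 2: 42, 28, 14 each | 7 of 9 |
| 3 | nine earlier at 56 or more; Group 3: 42, 28, 14 | 11 of 12 |
| 4 | twelve earlier past 28; 2A: 84, 70, 56, 42, 28, 14 | 17 of 18 (5 of 6 within 2A) |

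Review 2 improves to 8 of 9 if one of Groups 1B and 2 finishes at least 14 days before the other. Review 4 leaves out any adults already in Group 4. With a Month 1 cut at day 30, a group of three has 58, 44 and 30 days, so all pass day 28.

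**Exposure inside the gap.** If a review fell on day 14 itself, the next group's first member could be dosed that day and the second no earlier than 14 + 14 = day 28. Before day 28 that allows one person in Group 3 (after review 2), one child in Group 4 (after review 4), or one each in Groups 1B and 2 (after review 1). This follows the protocol's stagger list; SAP Section 4.1 omits Group 1B. Adult Group 4 has no stagger. The average planned pace is 27 / (30 × 30.44) × 14 = 0.4 participants per 14 days, or 0.5 if every cap is filled (3 + 3 + 3 + 6 + 3 + 15 = 33).

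**Processing lag.** Five business days are about 7 calendar days, which puts the last participant at day 21 before the summary is prepared. A lag adds time for symptom reports but no scheduled examination.

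**Primate dose by eye volume.** High: 4 × 10^11 / 2.5 = 1.6 × 10^11 vg/mL. Low: 4 × 10^10 / 2.5 = 1.6 × 10^10. Human highest: 6 × 10^11 / 5 = 1.2 × 10^11. Human lowest: 1 × 10^11 / 5 = 2 × 10^10. Group 2A: 3 × 10^11 / 5 = 6 × 10^10. The primate doses lie just outside the human range at both ends.

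**Denominators.** Six is the number injected per group. Section 1.1.4.3.2 also says half the animals were sacrificed at 14 days, which would leave 3 per group at Week 4, yet it follows all six vehicle animals to Week 4 and beyond. The haze counts (1, 3, 0) are firm; the percentages are less so.

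**The case against.** The strongest reply is that little may be left to change. Section 5.6 already cites inflammation in the first 12 subjects, which matches 3 + 3 + 3 + 3 in Groups 1A, 1B, 2 and 3, and the version 8.0 log entry cites a 12-month analysis. Reviews 1 to 3 are probably over, and perhaps all four. This stands and limits the point to any review still to come.

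Second, the plan has safeguards: the stagger in the next group, review of all accrued data, a floor that permits more data, discretionary extension, immediate symptom reporting (Section 5.4) and the halt after a DLT. The DSMC's advice led to steroid prophylaxis, and Group 2A was added because of observed inflammation. Adult Group 4 has no stagger, but its dose has already been tested. These measures shrink the gap, but none requires a scheduled examination of the last participant after Week 2. With Month 1 at day 30, a second person could be dosed on day 28, before that examination.

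Third, the primate signal may not carry over. The 3 haze cases at the high dose came from a per-volume dose above any human one. Inflammation improved over 2 months, with no apparent pressure effect and "no changes in ERG or visual evoked potential responses". Human results are in the Investigator's Brochure and the effect of steroids on timing is unknown. A related vector with a similar primate time course produced inflammation in 1 of 11 human subjects, at a lower dose, and it resolved on topical steroids. All this stands: the haze counts bracket the human doses and do not predict a human rate.

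**Conclusion.** The point holds as a modest safety improvement. Week 2 of the last participant is the minimum for all four reviews, and the protocol's own evidence places the vector-specific phase later. The gap is limited to one participant per review, or two at review 2 if Groups 1B and 2 finish together, and the stagger bounds who can be dosed before day 28.

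A reader might infer that the DSMC could see no inflammation, or that a dose was wrongly cleared. The documents support neither. The early phase and most participants' later phase fall within the data, actual reviews may have used more than the minimum, and no decision is shown to have turned on the missing visit.

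The counts assume the minimum stagger and a review at the earliest permitted cut. The relevance of day 28 assumes that human timing resembles primate timing, which cannot be checked here.

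**What to change.** For any review not yet held, above all review 4, make the last participant's Month 1 visit the minimum data in Sections 4.3, 5.6, 7.4.2 and 10.7.5. That visit already includes an eye examination, visual acuity, OCT and adverse-event review. Make no change for reviews already held.

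The cost is wording in four places and a delay of 14 to 16 days (2.0 to 2.3 weeks) per review. Even if all four remained, 4 × 14 to 4 × 16 days is 8.0 to 9.1 weeks, or 6% to 7% of about 130 weeks of enrollment. No visit or test is added. The downside is slower opening of the next group.
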